8.7 Clinical Laboratory Tests

Clinical laboratory tests will be performed at the time points listed in Section 22.1, Section 22.2 and Section 22.3 in a licensed clinical laboratory. A serum pregnancy test will be conducted at screening, while all remaining pregnancy tests will be urine pregnancy tests performed using a licensed test (dipstick). Subjects are to be in a seated or semi-recumbent position during blood collection.

The following clinical laboratory tests (Table 1) will be performed according to the Schedule of Events tables in Section 22.1, Appendix 1, Section 22.2, Appendix 2 and Section 22.3, Appendix 3.

Additionally, for Part III, fentanyl and oxycodone will be part of the UDS.

Confidential Page 42 of 108

INDV-2000 Indivior Clinical Study Protocol: INDV-2000-102 09 May 2023

Table 1 List of Laboratory Tests

Haematology
Haematocrit
Serum Chemistry:
Albumin

Haemoglobin Alkaline phosphatase

Mean corpuscular haemoglobin Alanine aminotransferase (ALT)

Mean corpuscular haemoglobin concentration Amylase

Mean corpuscular volume Aspartate aminotransferase (AST)

Platelet count Blood urea nitrogen

Red blood cell count Calcium

White blood cell count with differential (absolute count) Carbon dioxide

Urinalysis: Creatinine
Appearance Creatine kinase

Bilirubin Gamma-glutamyl transferase

Colour Glucose

Glucose Lactate dehydrogenase

Ketones Lipase

Leucocyte esterase Magnesium
Microscopic examination of sediment^a Phosphorus
Nitrite Potassium
Occult blood Sodium

Occult bloodSodiumpHTotal bilirubinProteinDirect bilirubinSpecific gravityTotal cholesterol

Urobilinogen Total protein
Triglycerides

Pregnancy:

Serum hCG Urine Drug Screen (UDS):

Urine hCG Opioids

Molecular Amphetamines
PCR for COVID-19 Cannabinoids
Barbiturates

Screening Only:BenzodiazepinesFSH (as needed in post-menopausal females only)MethamphetamineHaemoglobin A1cPhencyclidine

Hepatitis B surface Antigen

Hepatitis C Antibody

Ethanol

In addition to the above, for Part III:

HIV-1 and -2 antibodies Fentanyl
Prothombin Time with INR Oxycodone

Prothombin Time with INR Oxycodone PTT

Anti-HIV = human immunodeficiency virus antibodies; hCG = human chorionic gonadotropin; INR = international normalized ratio; and PTT = partial thromboplastin time.

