11 SERIOUS ADVERSE EVENTS

The Investigator or designee is responsible for identifying, documenting and reporting events that meet the definition of an SAE.

An SAE is any event that meets any of the following criteria:

- Death
- Life threatening
- In-patient hospitalization or prolongation of existing hospitalization
- Persistent or significant disability/incapacity
- Congenital anomaly/birth defect in the offspring of a subject who received INDV-2000
- Other: Important medical events that may not result in death, be life threatening or require hospitalization, may be considered an SAE when, based upon appropriate medical judgment, they may jeopardize the subject and may require medical or surgical intervention to prevent one of the outcomes listed in this definition. Examples of such events are:
 - o Intensive treatment in an emergency room or at home for allergic bronchospasm
 - o Blood dyscrasias or convulsions that do not result in in-patient hospitalization
 - o Development of study drug abuse or diversion
- Potential Hy's Law cases indicative of medication-induced hepatocellular injury, defined as:
 - o ALT $\ge 3x$ ULN and total bilirubin of $\ge 2x$ ULN (or INR > 1.5 if measured)
 - o ALT or AST >3x ULN with systemic symptoms (fatigue, nausea, vomiting, right upper quadrant pain or tenderness, fever, rash and/or eosinophilia [>5%])
- Potential Hy's Law cases should be managed as described in Section 22.4, Appendix 4.

An AE is considered "life threatening" if the subject was at immediate risk of death from the event as it occurred; i.e., it does not include a reaction that if it had occurred in a more serious form might have caused death. For example, study drug-induced hepatitis that resolved without evidence of hepatic failure would not be considered life threatening even though study drug-induced hepatitis can be fatal.

AEs requiring hospitalization will be considered SAEs. Hospitalizations for elective surgery or routine clinical procedures that are not the result of an AE (e. g., elective surgery for a pre-existing condition that has not worsened) should not be considered AEs or SAEs. If anything untoward is reported during the procedure, that occurrence must be reported as an AE (either 'serious' or 'non-serious') according to the usual criteria.

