22.4 APPENDIX 4 – Liver Safety

The following must occur if a subject meets any of the liver chemistry stopping criteria as outlined in Section 6.5 of the protocol:

- Subject must immediately be withdrawn from treatment. Do not re-challenge with study treatment.
- Notify the Indivior Medical Monitor or specified designee within 24 hours of learning of the abnormality.
- Completed the "Safety Follow-up Procedures" listed below.
- Upon completion of the safety follow-up, the subject must be withdrawn from the study unless further follow-up is required.

Subjects with ALT $\ge 3x$ ULN and bilirubin $\ge 2x$ ULN (>35% direct); or ALT $\ge 3x$ ULN and INR >1.5:

This event is an SAE and must be reported using the SAE Reporting Form (Section 11). Serum bilirubin fractionation should be performed, if testing is available. If fractionation is unavailable, urinary bilirubin is to be measured via dipstick (a measurement of direct bilirubin, which would suggest liver injury).

Make every reasonable attempt to have the subject return to the clinic within 24 hours for repeat liver chemistries, additional testing and close monitoring (with specialist or hepatology consultation recommended).

Monitor the subject twice weekly until liver chemistries (ALT, AST, alkaline phosphatase, bilirubin) resolve, stabilize or return to within baseline values.

Subjects with ALT $\geq 5x$ ULN or ALT $\geq 3x$ ULN who have hepatitis symptoms or rash, cannot be monitored for 4 weeks or have elevations that persist ≥ 4 weeks:

- Make every reasonable attempt to have the subject return to the clinic within 24-72 hours for repeat liver chemistries and additional testing.
- Monitor subject weekly until liver chemistries (ALT, AST, alkaline phosphatase, bilirubin) resolve, stabilize or return to within baseline values.

Subjects with ALT ≥3x ULN and <5x ULN and bilirubin <2x ULN, who do not exhibit hepatitis symptoms or rash:

• Contact the Indivior Medical Monitor within 24 hours of learning of the abnormality to discuss subject safety.

- Subject may continue study treatment, if liver chemistries (ALT, AST, alkaline phosphatase, bilirubin) can be monitored weekly for up to 4 weeks.
- If the subject later meets the liver chemistry stopping criteria (outlined in Section 6.5 of the protocol), immediately withdraw study treatment, perform additional testing and continue safety follow-up until liver chemistries resolve, stabilize or return to baseline values.

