- After 4 weeks of monitoring, if ALT <3x ULN and bilirubin <2x ULN, subject must be monitored twice monthly until liver chemistries normalize or return to within baseline values. Additional follow-up procedures for subjects who meet any of the stopping criteria:
- Viral hepatitis serology including:
 - o Hepatitis A Immunoglobulin M (IgM) antibody,
 - HBsAg and Hepatitis B Core Antibody (IgM),
 - o Hepatitis C RNA,
 - o Cytomegalovirus IgM antibody,
 - Epstein-Barr viral capsid antigen IgM antibody (or if unavailable, obtain heterophile antibody or monospot testing), and
 - Hepatitis E IgM antibody.
 - o Blood sample for PK analysis, obtained within 48 hours of last dose.
 - o Serum creatine phosphokinase and lactate dehydrogenase.
 - o Fractionate bilirubin, if total bilirubin $\geq 2x$ ULN.
 - Assess eosinophilia.
 - Record the appearance or worsening of clinical symptoms of hepatitis (fatigue, nausea, vomiting, right upper quadrant pain or tenderness, fever, rash or eosinophilia) as relevant on the AE eCRF.
 - o Record use of concomitant medications, acetaminophen, herbal remedies, other over-the-counter medications or putative hepatotoxins on the Concomitant Medications eCRF.
 - o Record alcohol use in the eCRF.
 - In addition, the following are required for subjects with ALT $\ge 3x$ ULN and bilirubin $\ge 2x$ ULN (<35% direct) but optional for other abnormal liver chemistries:

INDV-2000 Clinical Study Protocol: INDV-2000-102 09 May 2023

Anti-nuclear antibody, anti-smooth muscle antibody, Type 1 anti-liver kidney microsomal antibodies and quantitative total immunoglobulin G (IgG or gamma globulins).

Serum acetaminophen adduct High-Performance Liquid Chromatography (HPLC) assay (quantifies potential acetaminophen contribution to livery injury in subjects with definite or likely acetaminophen use in the preceding week James 2009]).

[figure not shown]
Indivior

[figure not shown]
Liver imaging (ultrasound, MRI, or CT) to evaluate liver disease. Data must be entered into the eCRF, if these tests are performed.

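### Protocol Appendix 4 requires three extra liver tests only at <35% direct bilirubin, leaving them optional for the >35% direct case in its own SAE tier

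*Protocol*

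**What the plan says.** Protocol Appendix 4 (Section 22.4) first sorts liver abnormalities into tiers. The top tier is ALT at least 3x ULN with bilirubin at least 2x "ULN (>35% direct); or ALT" at least 3x ULN with a raised INR. Of this tier the appendix says "This event is an SAE and must be reported using the SAE Reporting Form (Section 11". It also asks for return to the clinic within 24 hours, repeat and further testing, twice-weekly monitoring, and advises a hepatology opinion.

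The appendix then lists follow-up for subjects who meet a stopping criterion. The core items are viral serology, a PK sample, CPK and LDH, bilirubin fractionation, eosinophilia, and recording of symptoms, medicines and alcohol. Three further items follow: autoantibodies with total IgG, an acetaminophen adduct assay, and liver imaging. These are required for ALT at least 3x ULN with bilirubin at least 2x ULN at "<35% direct) but optional for other abnormal liver chemistries".

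Section 11 defines a potential Hy's Law SAE as ALT at least 3x ULN with total bilirubin at least 2x "ULN (or INR > 1.5 if measured", and gives no direct fraction. It adds that potential Hy's "Law cases should be managed as described in Section 22.4, Appendix 4".

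**The concern.** The two statements in Appendix 4 point in opposite directions. The tier that triggers SAE reporting is defined by a high direct fraction, while the extra work-up is compulsory only at a low one. A site following the text would have to order autoantibodies and imaging for a subject at <35% direct, and could leave them to discretion for a subject at >35%. No rationale for the low-fraction condition is given.

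What is at stake is the causality work-up of an individual liver case. Relatedness of TEAEs is part of the primary endpoint (Protocol Section 14.7.1), and Section 10.1.3 expects alternative causes to be investigated. Competing explanations are foreseeable: acetaminophen up to 2000 mg per 24 hours is permitted (Section 9.6.1), and Part III excludes subjects on transaminases only from 3x ULN upward (Section 5.3, criterion 28). Tests not done at the time of the injury may not be recoverable later.

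**Working it through.** No sample size, power or error rate is involved, so the check sets the provisions side by side.

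**1. Every direct-fraction threshold in Sections 6.5 and 22.4**

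| Place in the Protocol | Direct fraction |
|---|---|
| 6.5.1.1 individual stopping, Parts I and II | >35% |
| 6.5.1.2 cohort stopping, Parts I and II | >35% |
| 6.5.1.3 individual stopping, Part III | >35% |
| 6.5.1.4 study stopping | >35% |
| 22.4 SAE tier | >35% |
| 22.4 three added items | <35% |

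That is 4 + 1 = 5 uses of >35% against one of <35%. Only the two Appendix 4 entries concern the same ALT and bilirubin limits, so the direct comparison is one against one. The stopping criteria set bilirubin limits for a different purpose and are corroboration only.

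**2. Status of the three items when ALT is at least 3x ULN and bilirubin at least 2x ULN**

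| Wording | >35% direct | <35% direct |
|---|---|---|
| As written | optional | required |
| Condition deleted | required | required |
| Sign changed to >35% | required | optional |
| SAE under Section 11? | yes | yes |

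**3. Who reaches the list.** A subject who enters through the bilirubin stopping criterion has >35% direct by definition. As written, that subject can never be in the required group. The <35% group is not empty, because such a subject can enter on transaminases alone: above 3x ULN in Parts I and II, and above 5x ULN, or a doubling from a raised baseline, in Part III. Since Section 11 makes the pair an SAE, the subject can also enter through the SAE stopping criterion unless the event is clearly unrelated to IMP.

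**4. Does another provision make the items compulsory at >35%?** No. The SAE tier calls for further testing but names no tests. Section 11 only refers back to Appendix 4.

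**5. Size.** Three items are listed. The adduct assay is described for subjects with "definite or likely acetaminophen use in the preceding week", so 3 - 1 = 2 items (autoantibodies with IgG, and imaging) apply whatever the acetaminophen history. Planned enrolment is 48 + up to 16 = up to 64.

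**The case against.** The point turns on one inequality sign. A lone sign can be corrupted when a PDF is converted to text, and the layout around this list is disturbed. The other less-than and greater-than signs in Appendix 4 make clinical sense, so a misread is possible but not shown. This stands as a reason to look at the printed page first.

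The two statements can also both be obeyed: the tier governs reporting and monitoring, the list governs extra tests. That is fair. The fault is an implausible allocation of tests, not a strict impossibility. The remark on direct bilirubin, "a measurement of direct bilirubin, which would suggest liver injury", explains the urine dipstick used when fractionation is unavailable. It does not justify a 35% cut-off, so it lends only general support.

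A reader might infer that the sign is simply reversed and should be flipped. The documents do not establish that. Section 11 makes the same elevations an SAE at any direct fraction, so flipping the sign would withdraw an existing requirement from another group of SAE cases. Nor do the documents support reading the >35% case as going uninvestigated. The core list stays compulsory, return within 24 hours and close monitoring apply, a hepatology opinion is advised, and the three items remain permitted.

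**Conclusion.** The concern holds, at low severity. As written, Appendix 4 leaves three causality tests optional for the case it places in its own SAE tier, and the condition it uses instead matches neither that tier nor Section 11. The consequence is confined to the work-up of rare individual cases. SAE definitions and reporting, stopping rules, endpoints and the SAP are unaffected. The conclusion assumes that the printed protocol shows the less-than sign. If it shows >35%, the mismatch with the SAE tier disappears.

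**What to change.** Confirm the sign on the printed page. If it is <35%, delete the direct-fraction condition from the sentence introducing the three items, so that they are required for every subject with ALT at least 3x ULN and bilirubin at least 2x ULN. This matches Section 11 and takes nothing away from either group. If the sponsor means to limit the items to the Appendix 4 SAE tier, change the condition to >35% direct instead. The sponsor should then confirm that making them optional below 35% is intended, given that Section 11 also counts those cases as SAEs.

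The cost is one parenthesis or one sign in an amendment, with up to three already listed tests becoming compulsory in a rare case. There are no new scheduled visits, no change in sample size and no change to the SAP.

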22.5 APPENDIX 5 –Plasma PK Sampling Windows

22.6 APPENDIX 6- Toxicity Grading Scale for Healthy Adult and Adolescent Volunteers Enrolled in Preventive Vaccine Clinical Trials

Guidance for Industry

Toxicity Grading Scale for Healthy Adult and Adolescent Volunteers Enrolled in Preventive Vaccine Clinical Trials

Additional copies of this guidance are available from the Office of Communication, Training and Manufacturers Assistance (HFM-40), [name], or by calling [name] or [contact], or from the Internet at http://www.fda.gov/cber/guidelines.htm.

For questions on the content of this guidance, contact the Division of Vaccines and Related Products Applications, Office of Vaccines Research and Review at [contact].

> U.S. Department of Health and Human Services **Food and Drug Administration Center for Biologics Evaluation and** Research September 2007

Indivior

Table of Contents

IV	REF	FRENCES	8
	В.	Tables for Laboratory Abnormalities	6
		Tables for Clinical Abnormalities	
III.	TOX	CICITY GRADING SCALE TABLES	2
II.	BAC	KGROUND	2
I.	INTI	RODUCTION	1

Guidance for Industry

Toxicity Grading Scale for Healthy Adult and Adolescent Volunteers Enrolled in Preventive Vaccine Clinical Trials

This guidance represents the Food and Drug Administration's (FDA's) current thinking on this topic. It does not create or confer any rights for or on any person and does not operate to bind FDA or the public. You can use an alternative approach if the approach satisfies the requirements of the applicable statutes and regulations. If you want to discuss an alternative approach, contact the appropriate FDA staff. If you cannot identify the appropriate FDA staff, call the appropriate number listed on the title page of this guidance.

I. INTRODUCTION

Preventive vaccines are usually developed to prevent disease in a healthy population. The Office of Vaccines Research and Review, Center for Biologics Evaluation and Research, regulates preventive vaccines under authority of section 351 of the Public Health Service Act (42 U.S.C.262), as well as specific sections of the Federal Food, Drug, and Cosmetic Act, and reviews investigational new drug applications (INDs) and biologics license applications (BLAs). (See, for example, Title 21 Code of Federal Regulations (CFR) Parts 312, 600 and 601). Most of the clinical trials of preventive vaccines conducted to support INDs and BLAs enroll healthy volunteers in all phases of vaccine testing. The enrolment of healthy volunteers warrants a very low tolerance for risk in those clinical trials.

This guidance provides you, sponsors, monitors and Investigators of vaccine trials, with recommendations on assessing the severity of clinical and laboratory abnormalities in healthy adult and adolescent volunteers enrolled in clinical trials. The grading system described in the table can also be useful in defining a particular study's stopping rules (e.g., a certain number of adverse events, as defined in the table, may call for stopping the study). Less extreme observations (e.g., mild) may not require discontinuing the study vaccine but can still contribute to evaluating safety by identifying parameters to focus upon in subsequent product development. Uniform criteria for categorizing toxicities in healthy volunteers can improve comparisons of safety data among groups within the same study and also between different studies. We, FDA, recommend using toxicity grading scale tables, provided below, as a guideline for selecting the assessment criteria to be used in a clinical trial of a preventive vaccine. We recommend incorporation of such appropriate, uniform, criteria into the investigational plan, case report forms and study reports and correspondence with FDA, sponsors, monitors, Investigators and IRBs.

This guidance finalizes the draft guidance of the same title dated April 2005 (70 FR 22664, May 2, 2005).

Confidential Page 101 of 108

INDV-2000 Clinical Study Protocol: INDV-2000-102

FDA's guidance documents, including this guidance, do not establish legally enforceable responsibilities. Instead, guidances describe FDA's current thinking on a topic and should be viewed only as recommendations, unless specific regulatory or statutory requirements are cited. The use of the word *should* in FDA's guidances means that something is suggested or recommended, but not required.

II. BACKGROUND

Standardized toxicity assessment scales have been widely used to evaluate products treating specific diseases. For example, the National Cancer Institute's Common Toxicity Criteria Scale and the Division of AIDS' Toxicity Grading Scale standardize the evaluation of adverse events among patients with cancer and HIV/AIDS, respectively (Refs. 1, 2). The defined toxicity parameters in those scales are designed for patients who may already experience mild, moderate, or severe adverse clinical or laboratory events due to the disease process, and may not be appropriate for healthy volunteers.

In the development of the toxicity grading scales for healthy volunteers, we chose parameter limit values based on published information, when such values were available (Refs. 1-6). For example, the Brighton Collaboration has developed case definitions and guidelines to evaluate some adverse events associated with administering vaccines (Ref. 3). In some cases, parameter limit values were based on clinical experience and experience reviewing vaccine clinical trials that enroll normal healthy volunteers.

Toxicity grading scales for laboratory abnormalities should consider the local laboratory reference values when the parameter limit values are defined. The characterization of laboratory parameters among some populations of healthy adults and adolescents may require the exercise of clinical judgment, for example, consideration of the potential for ethnic differences in white blood cell (WBC) counts or gender differences in CPK values.

III. TOXICITY GRADING SCALE TABLES

Adverse events in a clinical trial of an investigational vaccine must be recorded and monitored and, when appropriate, reported to FDA and others involved in an investigation (sponsors, IRBs and Investigators). (See, for example, 21 CFR 312.32, 312.33, 312.50, 312.55, 312.56, 312.60, 312.62, 312.64, 312.66). Although the use of a toxicity grading scale for adverse events would not replace these regulatory requirements, using a scale to categorize adverse events observed during a clinical trial may assist you in monitoring safety and making required reports.

Nonetheless, we believe that categorization or grading of data as outlined in this document is supplementary to and should not replace full and complete data analysis.

These guidelines for toxicity grading scales are primarily intended for healthy adult and adolescent volunteers. The parameters in the tables below are not necessarily applicable to every clinical trial of healthy volunteers. The parameters monitored should be appropriate for the specific study vaccine. For some preventive vaccines under development, it may be appropriate Confidential

Page 102 of 108

to include additional parameters to be monitored during a clinical trial or to alter the choice of values in the toxicity table. For example, additional parameters might be added based on one or more of the following: safety signals observed in pre-clinical toxicology studies, the biological plausibility of the occurrence of certain adverse events, or previous experience with a similar licensed product.

Indivior

09 May 2023

As discussed above, the tables do not represent a recommendation to monitor all the listed parameters in all clinical trials of healthy volunteers, nor do the tables represent all possible parameters to be monitored. In addition, these tables do not represent study inclusion or exclusion criteria. We recommend that the parameters monitored be appropriate for the study vaccine administered to healthy volunteers participating in the clinical trial.

A. Tables for Clinical Abnormalities

Local Reaction to Injectable Product	Mild (Grade 1)	Moderate(Grade 2)	Severe (Grade 3)	Potentially Life Threatening (Grade 4)
Pain	Does not interfere with activity	Repeated use of non- narcotic pain reliever > 24 hours or interferes with activity	Any use of narcotic pain reliever or prevents daily activity	Emergency room (ER) visit or hospitalization
Tenderness	Mild discomfort to touch	Discomfort with movement	Significant discomfort at rest	ER visit or hospitalization
Erythema/Redness *	2.5 – 5 cm	5.1 – 10 cm	> 10 cm	Necrosis or exfoliative dermatitis
Induration/Swelling **	2.5 – 5 cm and does not interfere with activity	5.1 – 10 cm or interferes with activity	> 10 cm or prevents daily activity	Necrosis

^{*} In addition to grading the measured local reaction at the greatest single diameter, the measurement should be recorded as a continuous variable.

Confidential Page 103 of 108

^{**} Induration/Swelling should be evaluated and graded using the functional scale as well as the actual measurement.

Vital Signs *	Mild (Grade 1)	Moderate(Grade 2)	Severe (Grade 3)	Potentially Life Threatening (Grade 4)
Fever (°C) ** (°F) **	38.0 – 38.4 100.4 – 101.1	38.5 - 38.9 $101.2 - 102.0$	39.0 – 40 102.1 – 104	> 40 > 104
Tachycardia - beats per minute	101 – 115	116 – 130	> 130	ER visit or hospitalization for arrhythmia
Bradycardia - beats per minute***	50 – 54	45 – 49	< 45	ER visit or hospitalization for arrhythmia
Hypertension (systolic) - mm Hg	141 – 150	151 – 155	> 155	ER visit or hospitalization for malignant hypertension
Hypertension (diastolic) - mm Hg	91 – 95	96 – 100	> 100	ER visit or hospitalization for malignant hypertension
Hypotension (systolic) – mm Hg	85 – 89	80 – 84	< 80	ER visit or hospitalization for hypotensive shock
Respiratory Rate – breaths per minute	17 – 20	21 – 25	> 25	Intubation

^{*} Subject should be at rest for all vital sign measurements.

Confidential Page 104 of 108

^{**} Oral temperature; no recent hot or cold beverages or smoking.

^{***} When resting heart rate is between 60 - 100 beats per minute. Use clinical judgment when characterizing bradycardia among some healthy volunteer populations, for example, conditioned athletes.

Systemic (General)	Mild (Grade 1)	Moderate(Grade 2)	Severe (Grade 3)	Potentially Life Threatening (Grade 4)
Nausea/vomiting	No interference with activity or 1 – 2 episodes/24 hours	Some interference with activity or > 2 episodes/24 hours	Prevents daily activity, requires outpatient IV hydration	ER visit or hospitalization for hypotensive shock
Diarrhoea	2 – 3 loose stools or < 400 gms/24 hours	4 – 5 stools or 400 – 800 gms/24 hours	6 or more watery stools or > 800gms/24 hours or requires outpatient IV hydration	ER visit or hospitalization
Headache	No interference with activity	Repeated use of non- narcotic pain reliever > 24 hours or some interference with activity	Significant; any use of narcotic pain reliever or prevents daily activity	ER visit or hospitalization
Fatigue	No interference with activity	Some interference with activity	Significant; prevents daily activity	ER visit or hospitalization
Myalgia	No interference with activity	Some interference with activity	Significant; prevents daily activity	ER visit or hospitalization

Systemic Illness	Mild (Grade 1)	Moderate(Grade 2)	Severe (Grade 3)	Potentially Life Threatening (Grade 4)
Illness or clinical adverse event (as defined according to applicable regulations)	No interference with activity	Some interference with activity not requiring medical intervention	Prevents daily activity and requires medical intervention	ER visit or hospitalization

Confidential Page 105 of 108

B. Tables for Laboratory Abnormalities

The laboratory values provided in the tables below serve as guidelines and are dependent upon institutional normal parameters. Institutional normal reference ranges should be provided to demonstrate that they are appropriate

Serum *	Mild (Grade 1)	Moderate (Grade 2)	Severe (Grade 3)	Potentially Life Threatening (Grade 4)**
Sodium – Hyponatremia mEq/L	132 – 134	130 – 131	125 – 129	< 125
Sodium – Hypernatremia mEq/L	144 – 145	146 – 147	148 – 150	> 150
Potassium – Hyperkalemia mEq/L	5.1 – 5.2	5.3 – 5.4	5.5 – 5.6	> 5.6
Potassium – Hypokalemia mEq/L	3.5 - 3.6	3.3 - 3.4	3.1 - 3.2	< 3.1
Glucose – Hypoglycemia mg/dL	65 – 69	55 – 64	45 – 54	< 45
Glucose –				Insulin
Hyperglycemia	100 - 110	111 - 125	>125	requirements or
Fasting – mg/dL	110 – 125	126 - 200	>200	hyperosmolar
Random – mg/dL				coma
Blood Urea Nitrogen BUN mg/dL	23 – 26	27 – 31	> 31	Requires dialysis
Creatinine – mg/dL	1.5 – 1.7	1.8 - 2.0	2.1 – 2.5	> 2.5 or requires dialysis
Calcium – hypocalcemia mg/dL	8.0 - 8.4	7.5 - 7.9	7.0 - 7.4	< 7.0
Calcium – hypercalcemia mg/dL	10.5 - 11.0	11.1 – 11.5	11.6 – 12.0	> 12.0
Magnesium – hypomagnesemia mg/dL	1.3 – 1.5	1.1 – 1.2	0.9 – 1.0	< 0.9
Phosphorous – hypophosphatemia mg/dL	2.3 – 2.5	2.0 - 2.2	1.6 – 1.9	< 1.6
CPK – mg/dL	1.25 – 1.5 x ULN***	1.6 – 3.0 x ULN	3.1 –10 x ULN	> 10 x ULN
Albumin – Hypoalbuminemia g/dL	2.8 - 3.1	2.5 - 2.7	< 2.5	
Total Protein – Hypoproteinemia g/dL	5.5 – 6.0	5.0 – 5.4	< 5.0	
Alkaline phosphate – increase by factor	1.1 – 2.0 x ULN	2.1 – 3.0 x ULN	3.1 – 10 x ULN	> 10 x ULN
Liver Function Tests –ALT, AST increase by factor	1.1 – 2.5 x ULN	2.6 – 5.0 x ULN	5.1 – 10 x ULN	> 10 x ULN
Bilirubin – when accompanied by any increase in Liver Function Test increase by factor	1.1 – 1.25 x ULN	1.26 – 1.5 x ULN	1.51 – 1.75 x ULN	> 1.75 x ULN
Bilirubin – when Liver Function Test is normal; increase by factor	1.1 – 1.5 x ULN	1.6 – 2.0 x ULN	2.0 – 3.0 x ULN	> 3.0 x ULN
Cholesterol	201 – 210	211 – 225	> 226	
Pancreatic enzymes – amylase, lipase	1.1 – 1.5 x ULN	1.6 – 2.0 x ULN	2.1 – 5.0 x ULN	> 5.0 x ULN

^{*} The laboratory values provided in the tables serve as guidelines and are dependent upon institutional normal parameters. Institutional normal reference ranges should be provided to demonstrate that they are appropriate.

Confidential Page 106 of 108

^{**} The clinical signs or symptoms associated with laboratory abnormalities might result in characterization of the laboratory abnormalities as Potentially Life Threatening (Grade 4). For example, a low sodium value that falls within a grade 3 parameter (125-129 mE/L) should be recorded as a grade 4 hyponatremia event if the subject had a new seizure associated with the low sodium value.

^{***}ULN" is the upper limit of the normal range.

Hematology *	Mild (Grade 1)	Moderate (Grade 2)	Severe (Grade 3)	Potentially Life Threatening (Grade 4)
Hemoglobin (Female) - gm/dL	11.0 - 12.0	9.5 - 10.9	8.0 - 9.4	< 8.0
Hemoglobin (Female) change from baseline value - gm/dL	Any decrease – 1.5	1.6 – 2.0	2.1 – 5.0	> 5.0
Hemoglobin (Male) - gm/dL	12.5 – 13.5	10.5 – 12.4	8.5 - 10.4	< 8.5
Hemoglobin (Male) change from baseline value – gm/dL	Any decrease – 1.5	1.6 – 2.0	2.1 – 5.0	> 5.0
WBC Increase - cell/mm ³	10,800 - 15,000	15,001 - 20,000	20,001 - 25,000	> 25,000
WBC Decrease - cell/mm ³	2,500 - 3,500	1,500 – 2,499	1,000 – 1,499	< 1,000
Lymphocytes Decrease - cell/mm ³	750 – 1,000	500 – 749	250 – 499	< 250
Neutrophils Decrease - cell/mm ³	1,500 - 2,000	1,000 – 1,499	500 – 999	< 500
Eosinophils - cell/mm ³	650 - 1500	1501 - 5000	> 5000	Hypereosinophilic
Platelets Decreased - cell/mm ³	125,000 – 140,000	100,000 – 124,000	25,000 – 99,000	< 25,000
PT – increase by factor (prothrombin time)	1.0 – 1.10 x ULN**	1.11 – 1.20 x ULN	1.21 – 1.25 x ULN	> 1.25 ULN
PTT – increase by factor (partial thromboplastin time)	1.0 – 1.2 x ULN	1.21 – 1.4 x ULN	1.41 – 1.5 x ULN	> 1.5 x ULN
Fibrinogen increase - mg/dL	400 - 500	501 – 600	> 600	
